# The web-based survey

The web-based survey will include different outcome measures, which have been selected according to the relevant findings of previous cross-sectional studies and systematic reviews among the performing arts literature (Figure 2).

Each outcome measure correspond to a suspected factor that may be associated with the development of PRMDs.

The survey will start with questions about personal background and lifestyle (i.e. age, gender, self-reported weight and height, nationality, smoking status and sleeping habits), as well as practice habits (i.e. number of

hours of practice and years of experience) health history (i.e. major past injuries/accident/disorders and current medication) and health status (Self-Related Health - SRH).

Afterwards, in order to divide the cohorts, the presence of pain and/or MSK problems will be assessed through the following question: "When did you last experience a bout of significant pain and/or musculoskeletal problem?" with the following list of possible answers:

- 1. I currently have pain and/or a musculoskeletal problem (up to one month)
- 2. 2-3 months ago
- 3. 4-6 months ago
- 4. Up to 12 months ago
- 5. More than 12 months ago
- 6. I have never had any pain and/or musculoskeletal problem

[figure not shown]

Figure 2 Procedure of the web-based survey

According to the answer to this question, students will be addressed to different web pages throughout the survey (Figure 2):

- Respondents with a current pain and/or MSK problem (up to one month) will be asked questions to describe their current pain, to report their disability with Pain Disability Index (PDI), the Performing Arts

Section of Quick Disabilities of the Arm, Shoulder and Hand Outcome Measure (PAS –Quick DASH) and their pain self-efficacy with 2-item short form of the Pain Self-efficacy Questionnaire (PSEQ-2), as well as the Nordic Musculoskeletal Questionnaire (NMQ) for the assessment of musculoskeletal pain in the last 12 months

- Respondents without a current pain and/or MSK problem but a positive history of pain and/or MSK problem in the last 12 months (2-3 months ago, 4-6 months ago or up to 12 months ago) will be asked to answer the NMQ and questions on pain management to investigate how their pain and/or MSK problem has been treated
- Respondents without pain or with pain and/or MSK more than 12 months ago will be directly addressed to the next section

All respondents will be addressed to the next section, including the outcome measures:

International Physical Activity Questionnaire – short form (IPAQ-SF) for the assessment of physical status Kessler Psychological Distress Scale (K-10) for the assessment of anxiety and stress

Multidimensional Perfectionism Scale – short form (HFMPS-SF) for the assessment of perfectionism

The Chalder Fatigue Scale (CFQ-11) for the assessment of fatigue

Afterwards, all students (including those who will choose the sixth option) will be addressed to:

- International Physical Activity Questionnaire short form (IPAQ-SF) for the assessment of physical status
- Kessler Psychological Distress Scale (K-10) for the assessment of anxiety and stress
- Multidimensional Perfectionism Scale short form (HFMPS-SF) for the assessment of perfectionism
- The Chalder Fatigue Scale (CFQ-11) for the assessment of fatigue

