#### Research questions and hypotheses

Primary research question:

What are the main factors associated with increased risk of PRMDs in music students undertaking professional training?

Secondary research questions/objectives:

- 1. What is the prevalence of musculoskeletal disorders among university-level students in comparison with pre-college students?
- 2. Monitor and characterise the impact of the transition between pre-college and university-level music training on the development of PRMDs.
- 3. (Are there any differences in the severity and symptoms associated with PRMDs among music student groups at different levels of music training?)
- 4. Monitor and characterise the time course of PRMD development

- 5. (Are there significant differences in PRMD incidence between university-level students and pre-college students?
- 6. During training, do music students develop any type of musculoskeletal disorder that doesn't affect their ability to play at the level to which they are accustomed to?
- 7. Characterise health related quality of life and outcomes in music students at different stages of professional training.

Considering the aims and the research questions of the programme, the following hypotheses are formulated:

H1: The development of PRMDs is associated with a multitude of risk factors (i.e. age, gender, number of hours of practice, previous history of injury, poor physical status, psychological stress, perfectionism, fatigue) among music students.

H2: There is a higher prevalence of PRMDs among university-level students in comparison with precollege students.

H3: There is a higher prevalence of PRMDs among university-level students in the early stages of their training (transition between university-level and pre-college).

H4: University-level students develop more PRMDs over the years of their training than pre-college students.

H5: During their training, music students of both levels develop MSK disorders that affect their ability to play at the level they are accustomed to.

H6: Health and quality of life among music students is progressively poorer over the years of training (from the last two years of pre-college to the last years of Master-level)

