# Methodology

#### Study Design

This prospective longitudinal cohort study will be conducted through the following three phases (Figure 1):

- (1) A baseline cross-sectional survey to characterise the study population and subgroups, and form the basis for the evaluation of associated factors and relationships with the development of PRMDs;
- (2) A 6-months follow-up survey, and
- (3) A 12-months follow-up survey.

[figure not shown]

Figure 1 Research planning chart including main features of the cohort study

The study protocol has been approved by the Research Ethics Panel of the Queen Margaret University, Edinburgh (REP 0177).

After the first baseline data collection (Phase 1), the cohort of students will be broken down into:

- Cohort 1: music students (both pre-college and university-level) who are free of pain, PRMDs and/or MSK problems at baseline data collection
- Cohort 2: music students (both pre-college and university-level) who aren't free of pain, PRMDs and/or MSK problems at baseline data collection

Afterwards, the two cohorts will be followed and invited for reassessment at 6 months (Phase 2) and 12 months (Phase 3).

The 6-months and 12-months follow-ups for the Cohort 1 will be essential to monitor and record the development of new incidents of invasive pain, PRMDs and/or MSK problems within a period of a year and to enable characterisation of the nature and time course of developing pain, PRMDs and/or MSK problems.

The analysis of the results will attempt to answer primary research question and secondary research question 3 and 4, addressing the lack of any similar type of data in the current literature.

Similarly, the follow-ups for the Cohort 2 will be important in order to characterise the impact and time course of changes in any pain, PRMD and/or MSK problem within a 12-month period.

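### The one question that divides the cohorts is inconsistent on severity, so lesser musculoskeletal problems can be missed and Cohort 1 can include students who already have a complaint

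*Protocol*

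**What the plan says.** The Protocol, under The web-based survey, states that "in order to divide the cohorts, the presence of pain and/or MSK problems will be assessed through the following question". The question is "When did you last experience a bout of significant pain and/or musculoskeletal problem". Of the six answers, option 1 is "I currently have pain and/or a musculoskeletal problem (up to one month" (the bracket closes there), options 2 to 5 are time bands, and option 6 is "I have never had any pain and/or musculoskeletal problem".

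The answer decides what the student sees next. Option 1 leads to a pain description, the PDI, the PAS-QuickDASH, the PSEQ-2 and the NMQ. Students choosing options 2 to 4 "will be asked to answer the NMQ and questions on pain management". For options 5 and 6 the rule is: "Respondents without pain or with pain and/or MSK more than 12 months ago will be directly addressed to the next section". That next section holds the IPAQ-SF, K-10, HFMPS-SF and CFQ-11.

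Under Study Design, Cohort 1 consists of students "who are free of pain, PRMDs and/or MSK problems at baseline data collection". It is followed for new incidents over a year and serves the primary research question. Secondary question 6 asks: "do music students develop any type of musculoskeletal disorder that doesn't affect their ability to play at the level to which they are accustomed to".

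**The concern.** The stem sets a severity threshold. Options 1 and 6, the Cohort 1 definition and question 6 set none. How a lesser current problem is classified is therefore left to each respondent's reading of the item.

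Two things are at stake. Question 6 concerns disorders that do not affect playing, and at least some of these may be judged not significant. If those students skip the NMQ, their problems are not recorded. Second, Cohort 1 is the at-risk set for the risk-factor analysis. The Protocol's own Background objects to cross-sectional studies because distress may cause a PRMD or result from one. If Cohort 1 includes students with an existing complaint, the same ambiguity returns: distress or fatigue produced by that complaint at baseline can appear to predict a new event. Items skipped at baseline cannot be recovered by any later analysis.

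**Working it through.** The Protocol gives no figure to reproduce on this point, so the check is of the texts against each other, followed by an illustration on assumed values.

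**Severity threshold in each place**

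| Place | Threshold |
|---|---|
| Stem of the item | significant (may attach to pain alone or to both nouns) |
| Option 1 (current) | none |
| Options 2 to 5 (time bands) | none of their own; they take the stem's |
| Option 6 (never) | none; excludes any problem |
| Cohort 1 definition | none |
| Secondary question 6 | none |

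**Three students traced through the item**

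1. Current problem that the student calls significant: option 1, NMQ completed. Stem and option agree.
2. Last significant bout two years ago, lesser complaint now. By the stem, option 5 is truthful: the NMQ and all pain items are skipped. By the option wording, option 1 is also truthful: the NMQ is completed.
3. Only lesser problems ever, one of them current. Option 6 is untrue as worded. Option 1 is literally true but does not answer the stem. No option fits both.

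The Protocol does not map options to cohorts one by one. However, its skip rule groups option 5 with respondents without pain, so student 2 on the first reading would be placed in Cohort 1.

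**Can a skipped complaint be recovered?** The opening health-history items concern major past injuries, accidents or disorders and current medication, plus a general health rating. None of the four instruments in the common section is described as recording musculoskeletal symptoms. In Data analysis, the stated adjustment is for age, gender and instrument. The other listed variables include questionnaire scores, but a student who skipped the NMQ has no NMQ score. Nothing named would reliably recover the complaint.

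**Illustration (all inputs assumed; the documents give none of them)**

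- p = share of students with any current problem, 0.3 to 0.7
- f = share of those problems that are lesser, 0.2 to 0.4
- g = share of students with a lesser problem who choose option 5 or 6, 0 to 1

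Missed share of current problems = f × g. Share of Cohort 1 with an existing problem = p·f·g / (1 − p + p·f·g), taking Cohort 1 as students with no current problem plus those missed.

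| p | f | g | Missed share | Share of Cohort 1 |
|---|---|---|---|---|
| any | any | 0 | 0% | 0% |
| 0.3 | 0.2 | 0.5 | 10% | 0.03/0.73 = 4% |
| 0.5 | 0.4 | 0.5 | 20% | 0.10/0.60 = 17% |
| 0.7 | 0.4 | 1 | 40% | 0.28/0.58 = 48% |

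The result runs from nothing to nearly half of Cohort 1. It depends heavily on g, the respondents' reading of the item, which the text does not settle.

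**The case against.** The strongest reply is that option 1 is literally true for a student with a current lesser problem and leads straight to the NMQ. The routing rule for current problems also omits the word significant. A respondent who reads the options rather than the stem is classified correctly. This stands: a reader might infer that every such student is sent past the NMQ, and the documents do not support that.

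The word may also qualify pain only, leaving musculoskeletal problems of any degree in scope. That reading is possible, but a sole cohort-dividing item that allows both readings still has the defect.

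Nor is significant the same as limiting playing. A significant problem that leaves playing unaffected is captured by options 1 to 4. A reader might infer that question 6 is shown to be undercounted; the text supports only a possible partial undercount.

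Some threshold also fits the study's construct. The Background excludes mild transient aches from PRMDs, so a mild complaint that later impairs playing can properly count as a newly developed PRMD. That stands for the event count. It does not remove the reverse-causation problem for baseline distress and fatigue. The same Background passage says that musicians regard such aches as normal, which makes it plausible that some would not call them significant.

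Finally, the survey flow figure is not shown and the full questionnaire is not part of the Protocol text, so further pain items cannot be ruled out. The written skip rule nevertheless sends options 5 and 6 directly to the common section.

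**Conclusion.** The point holds as an inconsistency in the item that divides the cohorts. The stem carries a severity threshold that options 1 and 6, the Cohort 1 definition and question 6 do not. Lesser problems can be missed, question 6 can be partly undercounted, and Cohort 1 can contain students with existing complaints.

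The size cannot be estimated from the documents. It is zero if all affected students follow the option wording, and the percentages in the illustration rest wholly on assumed inputs.

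A reader might go further and conclude that Cohort 1 is in fact contaminated, or that every severity threshold must be removed from entry to it. The first is a possibility that the text does not establish. The second is a trade-off: the Background cites playing-related pain in 84% to 87% of first-year university music students (recall period not given), so a cohort free of pain of any degree could be much smaller. The change is worth making because it is cheap and protects baseline data that cannot be collected later.

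**What to change.** 1. State one severity threshold and use it in the stem, the answer options and the Cohort 1 definition.
2. Show the NMQ to all respondents at every survey, whatever the routing answer. Because the Protocol describes the NMQ as covering the last 12 months, add an item on current problems and a separate item on whether the problem affects playing.
3. Answer question 6 from respondents who report a problem without playing impact.
4. Keep Cohort 1 as defined by the stated threshold for the main risk-factor analysis. Repeat that analysis without students who report any current complaint at baseline, as a sensitivity analysis.

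This is an edit to wording and skip logic. It costs respondents without a recent bout a few more minutes, and the sensitivity analysis will rest on a smaller set.

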## Abstract/Summary of the research

Professional musicians are exposed to chronic high volume of continuous and repeated physical movements, sometimes in challenging and ergonomically unfavourable anatomical body positions, in order to acquire and improve technical playing skills. As a consequence, musicians are vulnerable to developing adverse playing-related musculoskeletal disorders (PRMDs) that may affect the manner in which and the extent to which music can be practised and performed.

In order to find out effective solutions for PRMDs and to develop future preventive measures, it is fundamental to firstly identify the main risk factors that play a significant role in the development of adverse musculoskeletal (MSK) conditions and symptoms.

The aim of the study will be to identify those factors associated with increased risk of PRMDs among music students. A further goal is to characterise and describe the clinical features of PRMDs, as well as determine the evolving course of PRMD's in music students during their professional training.

All pre-college and university-level students from several European music academies will receive an invitation to complete a web-based questionnaire survey at each of three occasions (baseline; 6-months follow-up; 12-months follow-up).

The web-based survey will include questions about any pain, PRMD and/or MSK problem they may have due to their musical practice, and different outcome measures (i.e. lifestyle and physical activity, practice habits, behaviour toward prevention and health history, level of stress, perfectionism, fatigue and disability).

To the best of our knowledge, no other longitudinal studies on risk factors for PRMDs have been conducted so far. Therefore, the study can be considered as an opportunity to fill the gaps of current research on PRMDs and generate new knowledge in educational and employment musical contexts.

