# Background/Rationale of the project

It has been shown that professions with high physical demands and/or frequently repeated movements like computer use are associated with a higher prevalence of MSK problems (Roquelaure et al. 2006; Sim et al. 2006; Cote et al. 2008). Similarly, professional musicians are exposed to chronic high volume of continuous and repeated physical movements and are vulnerable to developing adverse MSK conditions and symptoms (Kok et al. 2013; Chan and Ackermann 2014), that may affect the manner in which and the extent to which music can be practised and performed (Kok et al. 2013; Chan and Ackermann 2014). Indeed, this phenomenon was described by Zaza et al. (1998) as playing-related musculoskeletal disorders (PRMDs) and includes "any pain, weakness, numbness, tingling, or other physical symptoms that affect a musicians' capacity to sing or to play their instruments at the level they are accustomed to". This definition does not include mild transient aches or pains. In fact, according to Zaza et al. (1998), musicians use the words mild, just, slightest, normal and little to describe such aches and pains that would not be considered to be related to PRMD, because they don't affect the ability to play the musical instrument and are considered as "normal" as every-day pain (Zaza et al. 1998).

Current literature suggests that PRMDs do not only occur when entering the professional world, but are already present at the very beginning of musicians' professional education. A study reported that 25% of music students at university level, admitted that they had suffered from PRMDs, before starting their degree course (Spahn et al. 2004). Other cross-sectional studies have indicated that 43% of university-level students of music experienced a health problem related with their activity as musicians during the early stages of their education (Zaza 1992). Brandfonbrener

(2009) reported a playing-related pain prevalence between 84% and 87% among first year music students at university level and found that the majority had already suffered from PRMDs as pre-college students or even younger. Moreover, it has been shown that at least 45% of university-level students of music seek help from clinical professionals during their training because of PRMDs (Spahn et al. 2004; Williamon and Thompson 2006).

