#### Data analysis

Descriptive statistics will be used to investigate all the outcomes after the baseline data collection.

Furthermore, comparisons of gender, study, prevalence rate and hours of practice between pre-college and university-level students of music will be performed.

Baseline variables will be categorized to permit the calculation of risk ratios and the 95% confidence intervals (CI) for the development of PRMDs. Tests for trend of relative risk across categories will be carried out using the chi-square test. In order to check for confounders, logistic regression will be performed, adjusting for age, gender and different musical instrument.

Sample size estimation is reported in Figure 1.

Both the follow-ups will permit longitudinal change in outcome scores to be generated and compared (longitudinal comparisons) for strength and progression of association, alongside those from absolute outcome scores at several cross-sectional analyses.

For the evaluation of the association between the variables (gender, instrument group, age, years of playing, hours of practice, and questionnaires' scores) and pain, PRMD and/or MSK problem incidence, univariate analysis will be performed. Afterwards, all predictor variables that are significantly associated with the

occurrence of PRMDs will be included in a multivariate regression model to estimate the mutually adjusted effect of predictors on PRMDs.

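### The cohort-dividing item records only when a problem occurred, and no stated rule turns survey answers into a PRMD, so the risk-factor analysis alternates between any-cause pain and PRMDs

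*Protocol*

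**What the plan says.** The Abstract describes the survey as containing "questions about any pain, PRMD and/or MSK problem they may have due to their musical practice". The Background section adopts a definition of PRMD that turns on effect: "any pain, weakness, numbness, tingling, or other physical symptoms that affect a musicians' capacity to sing or to play their instruments", judged against the accustomed level. It leaves out mild, transient aches.

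The section on the web-based survey gives the dividing item this wording: "When did you last experience a bout of significant pain and/or musculoskeletal problem". Its purpose is cohort division. The six answers run from a current problem (up to one month) to never, and differ only in timing. The answer also routes the respondent:

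- Current problem: questions describing the pain, disability and self-efficacy scales, the performing-arts section of QuickDASH, and the Nordic questionnaire (NMQ).
- Problem within 12 months but not current: the NMQ and questions on pain management.
- Older problem or none: straight to the next section.

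Under Study Design, Cohort 1 consists of "music students (both pre-college and university-level) who are free of pain, PRMDs and/or MSK problems at baseline data collection". Its follow-up records new problems of the same broad kind and is meant to answer the primary question.

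The Data analysis section sets risk ratios for the development of PRMDs. It then relates a list of variables to "pain, PRMD and/or MSK problem incidence, univariate analysis will be performed", and carries predictors significantly associated with PRMDs into a multivariable model for PRMDs. The Data management section gives the same list of variables with PRMD incidence as the outcome.

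**The concern.** The study asks what raises the risk of PRMDs, but the only case-finding item whose wording is given captures any significant pain from any source. Headache, dental pain, a sprain from sport or a fall would all draw the same answer as a playing-related tendon problem. Such a student enters Cohort 2 at baseline, or appears as a new event in the Cohort 1 composite at follow-up.

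Two things are at stake. Predictors would be screened against one outcome and modelled against another. And if the composite stands in for PRMD, the prevalence and incidence figures and the risk ratios describe any-cause pain. An analysis plan written later can choose a rule, but it cannot recover an answer that was never requested.

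**Working it through.** The documents give no figure to reproduce: the sample size sits in Figure 1, which is not shown, and no incidence or effect size is stated. The check is a reading of the text followed by an illustration on assumed inputs.

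**Step 1: which outcome does each analysis use?**

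- Risk ratios: PRMDs (Data analysis).
- Univariate step: the composite (Data analysis), but PRMDs for the same variables in Data management.
- Selection into the multivariable model, and the model itself: PRMDs (Data analysis).

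No sentence links the composite to PRMDs.

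**Step 2: could a PRMD be derived from the items described?** It needs a musculoskeletal symptom with an effect on playing and, following the Abstract, a link to musical practice.

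- Current problem: possibly. The performing-arts QuickDASH section bears on playing, and the pain description may ask about cause, though its wording is not given.
- Resolved within 12 months: no. The NMQ is described only as assessing musculoskeletal pain, and the other questions concern treatment.

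The surveys are six months apart and a current problem reaches back one month. So a problem that began and ended in roughly the first five of those six months (6 − 1 = 5) falls in the second group.

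**Step 3: direction and size if the composite is the outcome.** Let p be the playing-related risk and b the risk of unrelated pain, assumed independent of p and equal in both exposure groups. The observed risk is 1 − (1 − p)(1 − b). Assume p = 0.20 exposed and 0.10 unexposed, a true risk ratio of 2.0.

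| b | Exposed | Unexposed | Observed ratio |
|---|---|---|---|
| 0.05 | 1 − 0.80 × 0.95 = 0.240 | 1 − 0.90 × 0.95 = 0.145 | 1.66 |
| 0.10 | 1 − 0.80 × 0.90 = 0.280 | 1 − 0.90 × 0.90 = 0.190 | 1.47 |
| 0.15 | 1 − 0.80 × 0.85 = 0.320 | 1 − 0.90 × 0.85 = 0.235 | 1.36 |
| 0.20 | 1 − 0.80 × 0.80 = 0.360 | 1 − 0.90 × 0.80 = 0.280 | 1.29 |

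The unexposed risk, 10% in truth, reads as 14.5% to 28%.

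**Step 4: effect on power.** Assume p = 0.30 versus 0.20 (true ratio 1.50), two-sided alpha 0.05 and equal groups. Then 294 per group give 80% power for the playing-related outcome.

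| b | Observed ratio | Power at 294 per group | n per group for 80% |
|---|---|---|---|
| 0.05 | 1.40 | 72.2% | 356 |
| 0.10 | 1.32 | 64.5% | 424 |
| 0.20 | 1.22 | 50.8% | 588 |
| 0.30 | 1.16 | 39.7% | 798 |

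**The case against.** The strongest reply is that the item is given only two jobs, dividing the cohorts and routing respondents, and is never said to define a PRMD. That is correct. A reader might infer that sports injuries and headaches are to be counted as PRMDs; the text supports this only for the univariate composite, and elsewhere simply leaves the PRMD rule out.

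A reader might also infer that the survey never asks about cause. The documents do not show that. The pain-description wording is not given and Figure 2 is missing, so a question on playing may sit there. It would reach only students with current pain, however, and no rule uses it to define a case.

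The breadth is deliberate. Secondary question 6 needs disorders that do not affect playing, and keeping students with any current pain out of the at-risk cohort is a conservative choice. Both points stand, so collecting all pain is not the fault. The NMQ could help set aside non-musculoskeletal pain, and injury history is collected, but neither has a stated part in case definition.

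Nor should one infer that every ratio is diluted. Hypothesis H1 also names previous injury, physical status, psychological stress and fatigue. These may themselves relate to unrelated pain, so their ratios could move either way.

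Finally, a cause item alone would not be enough. The adopted definition turns on effect on playing, so counting everything blamed on playing would admit the mild aches it excludes. This shapes the remedy and leaves the gap in place.

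**Conclusion.** The point holds in this form: the protocol names two outcomes for its risk-factor analysis, gives no rule leading from survey answers to a PRMD, and describes no item that would classify a problem that resolved between surveys. The first two follow from the text alone. The third rests on the items as described, and on the same routing being used at follow-up.

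The size is conditional on the composite being used as the outcome. PRMD frequency is then overstated, and ratios for practice hours or instrument are expected to shrink, from 2.0 to between 1.66 and 1.29 in the illustration. All the risks are assumed, as is unrelated pain that is equal across exposure groups. The direction is not claimed for distress, fatigue or physical activity. This should be settled before the surveys go out, because answers not requested cannot be recovered in analysis.

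**What to change.** Keep the broad item for dividing the cohorts and for secondary question 6. At all three surveys, ask everyone with a problem in the period, not only current cases, two short questions:

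1. Did it affect your capacity to play at your accustomed level?
2. What do you see as its main cause: playing or practice; sport, accident or other injury; other illness; unsure?

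Define a PRMD case as a musculoskeletal symptom that affected playing, excluding those attributed to a clear non-playing cause. Use this one outcome in the risk ratios, the univariate step and the multivariable model, and align the Data analysis and Data management wording with it. Report any-cause pain or musculoskeletal problems as a separate outcome. Add a sensitivity analysis that defines PRMD by effect on playing regardless of attributed cause.

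If the pain-description questions already cover these points, it is enough to extend them to resolved problems and to state the rule.

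The cost is one or two items per web survey and a few sentences in the protocol. The main drawback is that self-reported attribution may itself depend on practice hours, since students who practise more may blame playing more readily, which could inflate that ratio. The sensitivity analysis shows how far the result depends on attribution.

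### The question that divides the cohorts has answer options that are neither contiguous nor exclusive, so students near the current/not-current boundary can be misclassified

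*Protocol*

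**What the plan says.** The section The web-based survey states what the question is for: "in order to divide the cohorts, the presence of pain and/or MSK problems will be assessed through the following question". The stem is "When did you last experience a bout of significant pain and/or musculoskeletal problem". There are six answers:

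1. "I currently have pain and/or a musculoskeletal problem (up to one month"
2. 2-3 months
3. 4-6 months
4. "Up to 12 months ago"
5. "More than 12 months ago"
6. never

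The answer also sets the route through the survey. Option 1 leads to a description of current pain, the PDI, the PAS-QuickDASH, the PSEQ-2 and the NMQ. Options 2 to 4 share one branch ("2-3 months ago, 4-6 months ago or up to 12 months ago) will be asked to answer the NMQ"), with questions on pain management added. Options 5 and 6 skip both sets.

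The Study Design section defines Cohort 1 as students "who are free of pain, PRMDs and/or MSK problems at baseline data collection" and Cohort 2 as the rest. It ties the primary research question to the follow-up of Cohort 1. The text does not say which answer options make up each cohort. Figures 1 and 2 could not be read for this review, so a mapping shown only there would have been missed.

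**The concern.** The question decides who enters the at-risk group for the primary question, so its options need to place every student in exactly one category, above all at the line between current and not current. That line is where the wording is weakest.

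- Option 1 sets two conditions that can disagree. A student whose bout ended three weeks ago is inside the one-month window but does not have the problem now.
- A student whose bout ended six weeks ago is past option 1 and short of option 2.
- Option 4 has no lower bound, so it can be read as the next band after six months or as the whole of the past year.

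Two things are at stake. The first is the branch: a recovered student routed as current is asked to rate pain and disability that are no longer present, and misses the pain-management questions. The second is the cohort: if Cohort 1 is everyone without a current problem, the same answer moves the student into or out of the at-risk group. Because the wording is fixed at data collection, no later analysis can recover which meaning a respondent had in mind.

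**Working it through.** The plan gives no figure on this point to reproduce. The check sets time since the last bout against the printed options, treating option 1 as 0-1 month and varying the reading of option 4.

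| Reading | Months not covered | Months covered twice |
|---|---|---|
| Option 4 literal, 0-12 months | none | 0-1, 2-3, 4-6 (1 + 1 + 2 = 4 months) |
| Option 4 as more than 6, up to 12 | 1-2, 3-4 (2 months) | none |
| Option 4 as 7-12 | 1-2, 3-4, 6-7 (3 months) | none |
| Whole months, rounded up | none | none |

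Gaps and overlap thus belong to different readings and do not occur together.

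**Which of these change the branch**

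- Gap at 3-4 months: the neighbours are options 2 and 3, in the same branch. No effect.
- Gap at 6-7 months: the neighbours are options 3 and 4, in the same branch. No effect.
- Overlap of option 4 with options 2 and 3: same branch. No effect.
- Gap at 1-2 months: the neighbours are options 1 and 2, in different branches. The choice matters.
- Overlap at 0-1 month, with option 4 literal: options 1 and 4 are in different branches. The choice matters for a resolved bout.

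**The conflict inside option 1.** The table does not capture this, because it treats option 1 as a plain band. For a bout that resolved within the last month, the opening words of option 1 say no and the bracket says yes. The routing text does not settle it: the second branch is described as having no current problem but a history within 12 months, which fits this student, yet the options listed for it start at 2-3 months. Rounding to whole months does not help. The unclear zone for resolved bouts is therefore about 0-2 months.

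**Which change the cohort**

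- If Cohort 1 is options 2 to 6 (not current), the boundary at option 1 determines the cohort.
- If Cohort 1 is options 5 and 6 only (nothing in 12 months), options 1 to 4 are all in Cohort 2. The division between options 4 and 5 is clean, and the 0-2 month zone affects only the branch.

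**How many students might face the 1-2 month choice.** The documents give no distribution of recency, so this is illustration only. Among students whose last bout was more than 1 and up to 12 months ago:

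- Even spread: 1/(12 - 1) = 1/11 = 9%.
- Exponential recency with mean m months and S(x) = exp(-x/m): share = [S(1) - S(2)] / [S(1) - S(12)]. This gives 13% for m = 12, 18% for m = 6, 24% for m = 4 and 40% for m = 2.

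These are students exposed to a forced choice, not students misclassified. Those with a bout resolved in the last month come on top, and nothing in the documents allows a figure for them.

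**The case against.** The strongest reply is that the options work on an ordinary reading. In a list of recency bands, the bracket in option 1 is naturally taken as recency, and a student with long-standing pain will pick the option that opens with having it now. A respondent who rounds up to whole months meets neither gap nor overlap. Even when option 4 is read literally, a bout six weeks ago fits only that option, and its branch is the right one. Much of this stands: it shows that misclassification is possible, not that it happens. It does not cover the bout that resolved within the last month, and nothing tells respondents to round up.

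A reader might also infer that the options misdate new cases, since the survey is completed on three occasions and the follow-ups are meant to "monitor and record the development of new incidents of invasive pain, PRMDs and/or MSK problems within a period of a year". The documents do not support this. They state one purpose for the question, dividing the cohorts, and do not say that it dates incident cases. It asks about the last bout, not onset, so better bands alone would not date a new case. For the same reason, the uncovered months should not be turned into a percentage of lost cases: they are shares of calendar time.

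**Conclusion.** The point holds as a risk at one boundary. Students with a bout that resolved within about the last two months can be sent to the wrong branch. They can also be placed in the wrong cohort, provided Cohort 1 is defined as not current, which the text leaves open. The rest of the untidiness in the options does not change the branch. A reader might conclude that the cohorts are misclassified as the plan stands. The documents do not show that, because the outcome depends on how respondents read the options, and the size cannot be estimated without a recency distribution. The 9% to 40% range rests wholly on the assumed distributions and counts exposure to the 1-2 month choice only. The defect is modest, but it lies in the question that defines the at-risk group and cannot be repaired after data collection, so it is worth correcting.

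**What to change.** Before launch, replace the answer options with:

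- I have it now
- Not now, but within the last month
- More than 1 and up to 3 months ago
- More than 3 and up to 6 months ago
- More than 6 and up to 12 months ago
- More than 12 months ago
- Never

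State which survey branch the new within-the-last-month option follows, and which options form Cohort 1 and Cohort 2. Checked in the same way, contiguous bands cut at 1, 3, 6 and 12 months leave no gap, no overlap and no uncertain branch. Splitting the first band into now and not now keeps that property once the branch of the new option is stated.

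The cost is one edited online question with seven options instead of six, and a sentence or two in the Protocol.
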